7.3 Data Collection

Objective 2 will include two forms of data collection: 1) participant questionnaires at enrollment (baseline), midpoint (2-4 months), and endpoint (at least 6 months post enrollment) follow-up; 2) clinical and appointment data from the EHR. The baseline questionnaire will be administered to all participants at the time of consenting to participate in the study in order to collect basic sociodemographic characteristics, such as gender identity, education, marital status, income, residence, and other characteristics shown to influence ART outcomes (Mills et al., 2006). The questionnaire will also collect data on potential predictors of intervention success, including unmet needs, satisfaction with care and stigma. (Appendix F). At the midpoint (2-4 months post enrollment) and endpoint (at least 6 months post enrollment), the data will be collected again, using the same data collection instrument. The midpoint data collection and endpoint data collection target dates will be determined by study staff and participants at the first enrollment appointment. For Cohort 1 and Cohort 2 participants, these dates will coincide with their scheduled injections if possible, for convenience.

One week before each target data collection date, study staff will contact the participant using the preferred communication method they specified on their Locator Form at enrollment. Once a data collection date has been determined, study staff will contact participant through their preferred means of communication one day prior to appointment for a reminder.

At the time of data collection, the participant and study staff will meet at determined study location (either Project Trust or CID). Study staff will bring the Participant Folder, Log Book and a ClinCard. The participant will complete the participant survey. If the participant is in Cohort 1 or 2 and is scheduled to receive their

Protocol Title: **CAB-RPV LA Implementation Strategies for High-Risk Populations**

injection at this appointment, the survey can be completed during the 15-minute observation period after the injection.

The clinical and appointment data to be collected from the EHR on all study participants will include clinical endpoints (appointment adherence, viral load, CD4, etc.). Data on clinical endpoints will be collected from their EHR at enrollment at each data collection period using the Chart Review Tool (Appendix E).

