7.6 Injection Process and Safety Procedures

For patients enrolled in Cohort 1, injection procedures will be as follows:

- 15 minutes prior to the scheduled appointment time, the study clinician will remove the injection from refrigeration.
- Injections will be administered by a licensed healthcare professional (physician, nurse, nurse practitioner).
 - a. A complete dose will include two injections: one injection of cabotegravir and one injection of rilpivirine.
 - b. Each injection will be administered at separate gluteal injection sites during the same visit, with the ventrogluteal site recommended.
 - c. The clinician will consider the body mass index (BMI) of the patient to ensure that the needle length is sufficient to reach the gluteus muscle. Longer needle lengths (not included in the dosing kit) may be required for patients with higher BMI (greater than 30 kg/m²) to ensure that injections are administered intramuscularly as opposed to subcutaneously.
- The clinician and the participant will determine the target date for the next injection, which will occur between 25-32 days from initial injection. This discussion will happen while the participant waits for 15 minutes to ensure that no immediate adverse effects occur. This encounter and next planned injection date will be documented in the study Log Book by study staff. During this 15-minute period, the participant may also complete follow-up questionnaires if they are due for their three-month or six-month follow-up survey.
- Once the participant receives their second injection, they may discuss with their clinician whether they want to continue to receive their injection monthly, or whether they want to move to a bi-monthly schedule. The same procedures (confirming appointments in advance, removal from refrigerator, injection administration, monitoring period post-injection, scheduling of next injection, documentation in study log) will be used for follow-up injections
- Once the participant has been enrolled for at least 6 months in the study, they will be given the option to remain on CAB-RPV LA
 - a. That administration can take place either at PT or at CID depending on the participants preferences
 - b. If the participant wishes to receive their injection at CID, the study clinician will reach out to the participants CID provider so that the participant can begin to schedule their injections at CID

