10.0 Data Handling and Record Keeping

10.1 Confidentiality

At the screening consent appointment, participants will complete the HIPAA Authorization to grant permission to study staff to review their EHR. After an individual provides informed consent for screening and HIPAA authorization, a clinician will review their most recent labs for genotype and viral load, which would typically be part of standard care, to determine if they are eligible for CAB-RPV LA. Results of this review will be used to determine final eligibility. Following this, the EHR will be reviewed at 3 months and 6 months to document information needed to evaluate outcomes using the Chart Review Form. Other clinical and demographic information will also be abstracted to enable investigators to better characterize the study sample and to use as covariates in analyses. There will be no additional clinical records kept specifically for the study. As CAB-RPV LA is one standard of care for HIV, record of injections received will also be recorded in the EHR. All study data will be stored on a secure, password protected computer. Additionally, although no personal or identifiable data will be collected beyond the informed consent form, all documents created, such as those related to analyses and findings, will be maintained in a locked filing cabinet and in a password-protected database only accessible to the researchers.

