11.0 Statistical Plan

11.1 Study Hypotheses

Objective 2 has the following hypotheses:

- **H1:** Changing the service site will result in $\geq 80\%$ of participants in the community-based intervention arm beginning injections
- **H2:** Of participants in the community-based intervention arm who begin injections, 80% will complete 6 injections
- **H3:** Changing the service site will result in improved engagement in care for participants in the community-based intervention arm compared to matched controls (Cohort 3) at 6 months for intervention patients compared to control group patients
- **H4:** Changing the service site will result in superior HIV viral suppression at 6 months compared to for participants in the community-based intervention arm compared to matched controls (Cohort 3)
- **H5:** Participants in the community-based intervention arm will be equally satisfied with their care compared to patients who receive care in clinic settings (Cohort 2).

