11.2 Sample Size Calculation

For the pilot study, we have powered our study to address hypothesis 4 above. Our power calculation is as follows: With a total of 60 participants, 20 patients in each cohort, the study will have the statistical power to detect clinically meaningful differences in both engagement in care (appointment adherence) and undetectable viral load at 6 months. Depending on appointment adherence and undetectable viral load in the standard of care control group, we will be able to detect a minimum 40% difference, assuming 80% power and type 1 error probability (alpha) = 0.05. Estimates from our study sites suggest that undetectable viral load can be as low as 50% at any given time in our high-risk population. If we observe this level in the standard of care control group at 6 months, we will be able to observe a difference of 40% (or 90% vs. 50%) between the Cohort 1 CAB-RPV LA in the CBOc arm vs. the Cohort 2 CAB-RPV LA in the clinic arm and Cohort 1 CAB-RPV LA in the CBO arm vs. Cohort 3 no CAB-RPV LA arm participants, respectively. Because our intention to treat (ITT) analytic approach may mean an even lower proportion in controls (because missing data will be considered detectable), we believe our sample size is sufficient to yield rigorous clinical outcomes.

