11.3 Statistical Methods

We will first conduct exploratory analyses to assess the completeness and distributional properties of all variables, including an exploration of location (e.g., means for continuous variables and frequencies and percentages for categorical variables), spread (e.g., ranges, standard deviations), and shape (e.g., normal, skew). Missing baseline sociodemographic data will be imputed using single or multiple imputation technique if the proportion missing is $<10\%$ or $\geq 10\%$, respectively. After enrollment, we will compare dropout rates and characteristics of subjects who drop out or are lost to follow-up to assess potential for bias. In cases of missing viral load data, we will treat the result as detectable, in accordance with our primary ITT analytic approach, similar to other studies. Our primary analyses will be by ITT, but we will also conduct per protocol analyses via logistic regression models to estimate treatment effects.

Sociodemographic, behavioral, and clinical attributes at baseline will be compared between Cohort 1 and Cohort 2 and Cohort 1 and Cohort 3 using Chi Square and Fisher Exact test for categorical variables and T-test and Wilcoxon and Kruskal-

Protocol Title: **CAB-RPV LA Implementation Strategies for High-Risk Populations**

Wallis tests for continuous variables. Differences in engagement in care will be examined in two separate models to compare Cohort 1 vs Cohort 2 and Cohort 1 vs. Cohort 3. We will construct a multivariable logistic regression model with a logit link and the events/trials syntax to model the outcome. The inclusion of key baseline variables for adjustment will be based on a p value of ≤ 0.2 in the bivariate analysis or clinical significance. The following regression equation will be used:

$$\text{Engagement in care} = \alpha + \beta_1 * \text{ixgroup}_1 + \beta_2 * \text{factor}_1 + \dots + \beta_n * \text{factor}_n + \varepsilon,$$

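### H3's appointment-adherence model has no defined denominator, so visits due after a person leaves care can fall out of it and drop-out be under-counted, possibly unequally by cohort

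*Combined protocol and SAP*

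**What the plan says.** H3 in Section 11.1 predicts "improved engagement in care for participants in the community-based intervention arm compared to matched controls (Cohort 3) at 6 months". Section 11.2 ties the outcome to visits by naming "engagement in care (appointment adherence) and undetectable viral load at 6 months" as the two results the study can detect differences in. Section 11.3 then specifies a "logistic regression model with a logit link and the events/trials syntax to model the outcome" for engagement. Viral suppression, by contrast, is modelled as a dichotomous outcome.

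Neither the events nor the trials are defined, and no section says which appointments count. Section 11.3 calls the primary analysis ITT and treats a missing viral load as detectable. It gives no matching rule for engagement. Drop-out rates and the characteristics of people who drop out are to be compared separately.

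On data sources, Section 7.3 describes "The clinical and appointment data to be collected from the EHR on all study participants" and lists appointment adherence among them. For Cohort 1, Section 7.6 has the next injection date agreed at the injection visit and adds: "This encounter and next planned injection date will be documented in the study Log Book by study staff". Section 7.7 also places missed-dose outreach in the Log Book. Section 10.1 says that "record of injections received will also be recorded in the EHR". No section says whether the EHR also holds Cohort 1's missed injection appointments, or whether the Log Book feeds the H3 analysis.

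**The concern.** An events/trials model takes a count out of a count for each person. With appointment adherence as the outcome, most analysts would use visits kept over visits scheduled. On that reading a person who leaves care soon stops having visits scheduled, so the remaining months add no failures. A person with nothing booked has zero trials and contributes nothing to the likelihood, so is lost from an analysis that is meant to be ITT. A correction for overdispersion does not bring those visits back.

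The effect need not be equal across cohorts. Cohort 1 has monthly or bi-monthly injection dates set one at a time (Sections 7.1 and 7.6). Cohort 3 has access to regular clinic appointments but no stated schedule, so its denominator is whatever happened to be booked.

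Section 4.1 names dropping out of care as the primary risk of participation, and H3 is the hypothesis that compares engagement between cohorts. If the outcome registers drop-out weakly, or differently by cohort, the comparison does not answer its own question. An undefined denominator can also be chosen after the data are seen.

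**Working it through.** **1. The plan's own figure.** Section 11.2 states: "With a total of 60 participants, 20 patients in each cohort". It says the study can "detect a minimum 40% difference, assuming 80% power and type 1 error probability (alpha) = 0.05", with 90% against 50% as the example. With p1 = 0.5, p2 = 0.9, mean 0.7, two-sided alpha 0.05 and 80% power:

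n = [1.96 × √(2 × 0.7 × 0.3) + 0.842 × √(0.5 × 0.5 + 0.9 × 0.1)]² / 0.4² = (1.270 + 0.491)² / 0.16 = 19.4, so 20 per cohort.

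Power at 20 per cohort is 81.3%. The figure reproduces and is not in dispute. It is a calculation on one yes/no result per person, whereas Section 11.3 analyses engagement as a count out of a count.

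**2. Inputs for the illustration.** The documents give no drop-out rate and no visit count for Cohort 3, so these inputs are assumed: 20 people in a cohort, 6 due visits each (120 in all), 90% of visits kept while in care, and d people leaving after 2 visits. Let m be the number of missed visits recorded per leaver before scheduling stops.

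- Kept visits = (20 − d) × 6 × 0.9 + d × 2 × 0.9
- Scheduled visits = (20 − d) × 6 + d × (2 + m)
- Fixed denominator = 120

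**3. Results.**

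| Leavers d | Kept | No miss recorded (m = 0) | One miss each (m = 1) | All 120 due visits |
|---|---|---|---|---|
| 2 | 100.8 | 100.8/112 = 90.0% | 100.8/114 = 88.4% | 84.0% |
| 4 | 93.6 | 93.6/104 = 90.0% | 93.6/108 = 86.7% | 78.0% |
| 8 | 79.2 | 79.2/88 = 90.0% | 79.2/96 = 82.5% | 66.0% |
| 10 | 72.0 | 72.0/80 = 90.0% | 72.0/90 = 80.0% | 60.0% |

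With d = 8 and two recorded misses each, the result is 79.2/104 = 76.2%. So with eight leavers, adherence is overstated by 24.0, 16.5 or 10.2 points for m = 0, 1 or 2.

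**4. Effect on a comparison of two cohorts (same assumptions).**

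- Different retention, no misses recorded: 8 leavers in one cohort and 2 in the other give 90.0% in both. On all due visits they give 66.0% and 84.0%, an 18-point difference that is not seen.
- Identical retention, unequal recording: 8 leavers in each, with no miss recorded in one cohort and one per leaver in the other, give 90.0% and 82.5%. That 7.5-point gap comes from recording alone.

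**5. Effect of incomplete capture of misses.** Suppose 20% of 120 due visits are missed (96 kept, 24 missed). Full capture gives 96/120 = 80.0%, half capture gives 96/108 = 88.9%, and no capture gives 100%. With 40% missed (72 kept, 48 missed) the figures are 60.0%, 72/96 = 75.0% and 100%.

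**6. Due visits differ by schedule.** The Section 7.0 table gives 4 injections by month 7 on the bi-monthly schedule, and 6 or 7 on the monthly one, depending on the oral lead-in. A denominator therefore has to follow the schedule each person is on.

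**The case against.** Kept-over-scheduled is nowhere written. The same model runs equally well with a fixed number of planned visits per person, and the Section 7.0 table could supply them for Cohort 1. That is correct, and it makes the point conditional. But the plan does not adopt the fixed version, and it offers no schedule from which to build one for Cohort 3.

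A reader might infer that Cohort 1's missed dates are absent from the EHR. The documents do not show this. Section 7.3 collects EHR appointment data on all participants, and Section 10.1 says that injections received are also in the EHR, not that only those are. The injecting clinicians are hospital staff (Section 6.0) who prescribe through its EHR (Section 7.5). What stands is that the Log Book is named for planned dates and missed-dose outreach, and that EHR capture of the misses is not stated.

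A reader might also infer that drop-out disappears from the result. That is too strong. Every recorded miss counts as a failure, and many participants keep their usual infectious disease provider (Section 7.11), so a leaver may miss several booked visits. Section 11.3 compares drop-out separately, H2 counts Cohort 1 leavers who do not complete their injections as failures, and H4 treats missing viral load as detectable. These limit the harm but do not repair H3: the drop-out comparison does not enter the H3 estimate, H2 concerns only Cohort 1 participants who began injections, and H4 measures something else.

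Nor does the plan contradict its ITT principle. It is silent on how ITT applies to engagement.

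**Conclusion.** The point holds in a conditional form. The trials in the H3 model are undefined, nothing keeps visits due after departure in the denominator, and engagement has no counterpart to the viral-load rule. On the natural reading, drop-out is under-counted, and possibly unequally between Cohorts 1 and 3. The direction of any bias between cohorts cannot be told from the documents: incomplete capture of Cohort 1 misses would favour Cohort 1, and Cohort 3 leavers with nothing booked would favour Cohort 3.

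In the illustration with eight of 20 leaving, adherence reads 90.0%, 82.5% or 76.2% with zero, one or two recorded misses per leaver, against 66.0% when every due visit counts. These sizes rest on assumed visit counts, attendance and drop-out. They show how far the choice of denominator can move the result and do not forecast it. The sample size in Section 11.2 is unaffected. The change should be made before outcome data are examined.

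**What to change.** In Section 11.3, define for every enrolled participant the visits due over a fixed six-month window, using the visit interval in force. For Cohort 1 this is the last agreed monthly or bi-monthly schedule. It cannot be fixed once at enrolment, because that choice is made later. For Cohort 3 it is the clinic's routine follow-up interval, which the plan should state. Count due visits after loss to follow-up as not kept, and keep all 20 per cohort in the primary ITT analysis. Apply one rule for ascertaining missed visits in every cohort, and check Cohort 1's EHR appointments against the Log Book. Using the Log Book for Cohort 1 alone would itself make the sources unequal.

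Alternatively, use one yes/no outcome per participant, the unit behind the Section 11.2 calculation, with a criterion stated in advance that requires kept visits late in the window. Counting only people with no kept visit as not engaged would not be enough, because someone who attends once and leaves would pass.

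The cost is a few sentences in Section 11.3 and an extract of an existing log. The yes/no version gives up some visit-level detail, which can stay descriptive.

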7.2 Cohorts 2 & 3 Recruitment, Screening & Enrollment

Cohort 2 Recruitment and Enrollment: Participants for Cohort 2 will be individuals who are receiving HIV in care at BMC's Center for Infectious Diseases (CID) and are receiving CAB-RPV LA. CID pharmacists and providers will approach all individuals who are actively receiving CAB-RPV LA and assess whether they are interested in participating and ask them to complete the Screening Consent (Appendix C). If individuals are interested in participation, they will be given a warm handoff to study staff. Study staff will meet with patients at CID to complete the enrollment consent form (Appendix D). Participants will also be asked to complete the participant questionnaire at the baseline, midpoint (2-4 months post baseline) and endpoint (at least 6 months post baseline). They will also be asked to complete the Locator Form (Appendix F). Participants will enter the cohort and contribute data to the study from their first CAB-RPV LA injection and be followed in the EHR for a period at least 6 months to determine engagement in care and adherence. Data on clinical endpoints (appointment adherence, viral load, CD4, drug use etc.) will be collected from the EHR.

Cohort 3 Recruitment and Enrollment: EHR data will be used to match patients for Cohort 3 1:1 to patients in Cohort 1 based on the following variables: history of drug use, housing status, sex. Patients in cohort 3 will be a prospective cohort of patients who are HIV positive and not receiving CAB-RPV LA. The Clinical Data Warehouse will match 10 participants to every 1 enrolled in Cohort 1 based on the variables above. CID staff will approach potential participants to assess interest in participation. If individuals are interested in participating, they will be given a warm handoff to the project manager to complete the Enrollment Consent form (Appendix D). They will also be asked to complete the Locator Form (Appendix G). The remainder of their study activity will mirror that of Cohort 2.

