where ixgroup_1 is a dummy variable for cohort assignment, α is the intercept, $\beta_1, \beta_2, \dots, \beta_n$ is a vector of possible coefficients, and ε is an error term. Similarly to examine adherence we will use a multivariable logistic regression with a dichotomous outcome for undetectable viral load status at 6 months. Potential confounders will be examined using methods described above and entered into the final model based on a p value of ≤ 0.2 or clinical significance. We will conduct stratified analyses based on gender and other risk attributes (e.g. homelessness, substance use, etc.), though this will be exploratory, given the cohort study's pilot nature and our sample size.

12. Budget Justification

Our total enrollment into Objective 2 remains 60 participants. Therefore, the resources necessary to accomplish the scope remain unchanged, and we are not requesting a budget increase.

13. Ethics/Protection of Human Subjects

This study will be conducted according to applicable US federal regulations and institutional policies (which are based in federal regulations, guidance, and ICH Good Clinical Practice guidelines). This protocol and any amendments will be submitted to the Boston Medical Center/Boston University Medical Campus IRB, for formal approval of the study conduct. The decision of the IRB concerning the conduct of the study will be made in writing to the investigator.

All subjects for this study will be provided a consent form describing this study and providing sufficient information for subjects to make an informed decision about their participation in this study. The consent form will be submitted with the protocol for review and approval by the IRB. The consent of a subject, using the IRB-approved consent form, must be obtained before that subject is submitted to any study procedure. Consent will be documented as required by the IRB.

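### The covariate rule names no covariates and sets no cap, and ordinary logistic regression is fragile with about 12 detectable results in the H4 comparison

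*Combined protocol and SAP*

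**What the plan says.** Section 11.3 describes two kinds of logistic model. For engagement in care (events/trials form): "The inclusion of key baseline variables for adjustment will be based on a p value of" 0.2 or less in bivariate analysis, or on clinical significance. The viral-load model takes over the same rule: "Potential confounders will be examined using methods described above and entered into the final model based on a p value of" 0.2 or less, again with clinical significance as the alternative route.

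The regression equation shows only generic factors numbered up to n. The section names no covariates and sets no maximum. It does not say whether the bivariate test is against cohort or against outcome, and it does not define clinical significance. It gives no method for sparse cells or separation.

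Section 7.2 sets out the matching step, done from health records: "match patients for Cohort 3 1:1 to patients in Cohort 1 based on the following variables: history of drug use, housing status, sex". Section 11.3 lists none of these as covariates and does not mention the matched pairs. Gender, homelessness and substance use appear there only as strata for exploratory analyses.

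Section 11.2 says "we have powered our study to address hypothesis 4 above", which is viral suppression at 6 months in Cohort 1 against Cohort 3, and gives the size as "With a total of 60 participants, 20 patients in each cohort".

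**The concern.** Two separate weaknesses meet in the model that carries the one powered hypothesis.

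First, covariates are chosen after the data are seen, by a screen or by an undefined judgement. Two analysts could follow the text faithfully and report different H4 estimates, and neither would be obliged to adjust for the factors on which Cohort 3 was built.

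Second, maximum-likelihood logistic regression behaves poorly with few events and an open-ended covariate list. Fits can fail to give a finite odds ratio, standard errors grow, and estimates drift away from zero. The 80% power in section 11.2 is a two-proportion figure and does not describe that model.

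**Working it through.** **Inputs from section 11.2.** 20 per cohort; 90% against 50% undetectable ("we will be able to observe a difference of 40% (or 90% vs. 50"%); "assuming 80% power and type 1 error probability (alpha) = 0.05". Sidedness is not stated; two-sided is assumed.

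**1. The plan's own figure.** With pooled variance and mean proportion 0.70:

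z = (0.40 × √20 − 1.96 × √(2 × 0.70 × 0.30)) / √(0.09 + 0.25) = (1.789 − 1.270) / 0.583 = 0.89, so power is 81.3%.

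The required n is 20 per cohort, so the stated figure reproduces. Exact power is 83.8% for the uncorrected chi-square test and 74.2% for Fisher.

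**2. Events.** 20 × 0.10 + 20 × 0.50 = 2 + 10 = 12 detectable results (5th to 95th percentile 8 to 16). With cohort plus three covariates, 12 / 4 = 3 per coefficient.

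**3. No finite odds ratio.** The chance of no detectable result in Cohort 1 is 0.9^20 = 12%. This arises before any covariate is added.

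**4. What the p-value route does to the matching factors.**
- Screen against cohort: exactly matched factors give p = 1 and always fail. With independent cohorts of equal prevalence, each factor passes 10–22% of the time.
- Screen against outcome, with assumed prevalences 0.70, 0.50 and 0.25:

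| Odds ratio per factor | Single factor kept | All three dropped |
|---|---|---|
| 1 | 9–16% | 61–74% |
| 2 | 17–28% | 38–52% |
| 3 | 26–44% | 21–33% |
| 4 | 33–54% | 14–23% |

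With a chi-square screen, at least one of the three is dropped in 88–99% of trials across these odds ratios.

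**5. Stability of ordinary fits** (exact 1:1 matching, odds ratios 1 to 4).
- No finite estimate: 11–14% with cohort alone, 21–36% with the three factors, 24–43% with three further covariates.
- Median standard error of the cohort log odds ratio: 0.87, then 0.92–1.09, then 1.09–1.27.
- The planning log odds ratio is ln 9 = 2.20. With the three factors included but unrelated to outcome, the mean among estimable fits is 2.39.

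**6. Power.** Assumptions not in the documents: the prevalences above, two matching factors with log odds ratio 0.8, and seven noise covariates (prevalence 0.40 in the first run). The first run had 1,500 trials; the second is a repeat of the same kind. Fits without a usable estimate count as non-significant. The share of such fits is in brackets.

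| Analysis | First run | Second run |
|---|---|---|
| Cohort only, Wald | 68% (13%) | not run |
| p ≤ 0.2 screen, Wald | 54% (27%) | 57% (21%) |
| Three fixed factors, Wald | 62% (24%) | 63% (21%) |
| p ≤ 0.2 screen, Firth | 77% | 74% |
| Cohort only, Firth | 82% | 79% |
| Three fixed factors, Firth | 84% | 80% (0%) |

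- Selection: 62 − 54 = 8 and 63 − 57 = 6 points with Wald; 84 − 77 = 7 and 80 − 74 = 6 with Firth. Against cohort-only Firth it is 82 − 77 = 5 and 79 − 74 = 5.
- Estimator: 84 − 62 = 22 and 80 − 63 = 17 points with three fixed factors; 82 − 68 = 14 with cohort only.
- Adding the three factors to cohort-only Firth: 84 − 82 = 2 and 80 − 79 = 1.

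Screening against cohort instead gave 62–65% Wald power with 15–16% of fits not estimable. With no prognostic effect, or with log odds ratio 1.2 for all three factors, screened Wald power was 56–65% against 83–87% for fixed-factor Firth. Type I error was 4–6% under the screen and 4.3–5.2% for fixed-factor Firth.

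**The case against.** A reader might infer that the plan will usually discard the three matching factors. The text does not support that. Clinical significance is an alternative route, so those factors can enter whatever their p-values. Step 4 describes the p-value route alone. The natural reading of that route is a screen against cohort, because the only bivariate tests described before the rule compare cohorts at baseline, but the plan does not say so. What stands is that nothing requires the factors to be kept, and that the undefined clause can be applied after the data are seen.

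A reader might also credit the whole gap between screened Wald and fixed-factor Firth to the screen. That contrast changes two things at once, and step 6 shows that most of it is the estimator. Nor does dropping matching factors cause the instability. A smaller model is more stable, and the trouble comes from 12 events and an uncapped list. Fixing the three factors in an ordinary fit still leaves 21–24% without an estimate.

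Three further points are fair. The 12 events belong to the viral-load model, not to the engagement model. Section 11.3 counts missing viral loads as detectable, which could raise the count above 12 and lower the 12% figure. And the section names no test: Wald is assumed here as the usual default. A likelihood-ratio test might recover some power, but it would not supply a finite odds ratio.

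**Conclusion.** The point holds as a lack of pre-specification together with an unsuitable default estimator. It should be corrected before analysis.

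The 12 events and the 12% chance of no finite odds ratio follow from the plan's own rates. The 21–27% of outcome-screened or three-factor ordinary fits without an estimate, and the 54–63% Wald power, rest on assumed prevalences and effects that the documents do not give. The range was 21–36% for three-factor fits when the odds ratios ran from 1 to 4. The pattern was stable over the settings tried: roughly 5–8 power points lost to selection and 14–23 to the estimator (the upper end being 77 − 54 = 23 under the screen).

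The results do not support a claim of false-positive inflation. They also do not show that adjusting for the matching factors adds much power. The case for fixing those factors is that they reflect the design and make the estimate reproducible.

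**What to change.** In section 11.3:

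- Delete the p ≤ 0.2 rule and the undefined clinical-significance clause from both models.
- For the Cohort 1 versus Cohort 3 viral-load model, pre-specify cohort, history of drug use, housing status and sex. Fit by Firth penalised likelihood, with a penalised likelihood-ratio test and profile confidence intervals. Report the cohort-only Firth estimate alongside.
- For Cohort 1 versus Cohort 2, name a short covariate list on clinical grounds and use the same estimator. Cohort 2 is not matched, so the three factors have no design basis there.
- Put other imbalances in named sensitivity analyses. Baseline viral suppression must be among them, because sections 5.1 and 5.2 require it of Cohort 1 but not of Cohort 3.
- State covariates in advance for the engagement models as well. The 12-event argument does not apply to them.

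The cost is SAP wording: drug use, housing and sex are already drawn from the EHR for matching. The drawback is that the primary model leaves other imbalances unadjusted. In a non-randomised comparison the sensitivity analyses must therefore be reported next to it.
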